Aim 2: For examining mediation/mechanistic effects at the individual-level from longitudinal data via parallel process growth models (paths from treatment assignment to individual-level slope of mediator to individual-level slope of outcome), with 120 individuals, there will be 80% power to detect indirect effects comprised of a small-medium effects of the intervention arm on latent slope of mindfulness (defined as a correlation of 0.25 between variables or equivalently as explaining 6% of the variance in the latent mindfulness slope) and a medium effect of the slope of mindfulness on the slope of the outcome (defined as a correlation of 0.36 or equivalently as explaining 13% of the variance of the outcome). For examining mediation/mechanistic effects at the weekly level, power is less clear. Although DSEM combines aspects of more familiar modeling techniques, it is new and thus limited information is available on determining power for such models. In one set of simulation studies, good model performance was observed for several models differing in complexity for a sample size of 200 individuals with a number of observations per individual ranging from 20-200, and good model performance for all but the most complex models for smaller sample sizes. Thus, with data from 120 individuals contributing up to 8 observations each, we expect to have enough data to accomplish the aim of understanding the mechanisms underlying the intervention effects of MMORE. We will conduct weekly assessments to minimize participant burden. This strategy will still allow us adequate sampling frequency to track changes in outcome measures over the course of treatment. The power

calculations for the mechanistic effects were based on individual-level latent slope variable estimates and are thus not affected by a change to the number of indicator variables for the latent slope variables (reduced from 70 daily assessments to 8 weekly assessments). Power calculations for the dynamic SEM models are approximate and were not specifically based on having daily assessments per individual so will also not change.

Aim 3 is exploratory and not powered.

Treatment Assignment Procedures

Randomization will be conducted via permuted blocks. Once 8-10 participants have enrolled, an intervention will commence for that cohort. The randomization block size would be random, with blocks of size 4, 6, and 8. We plan ongoing recruitment and to start a new group approximately every 8 weeks.

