framework that allows for estimating simultaneous sets of equations involving latent and observed variables, thus allowing modeling of multi-level data, and modeling relationships at each level including mediation. Unlike non-dynamic SEM, however, DSEM have the capability to estimate time-series model(s) at the within-individual level, and also allow for a between-time level model (in addition to the between-individual level model) to incorporate time-varying effects observed in intensively collected data (i.e. creating a cross-classified model). Thus DSEM combine the advantages of time-series models, multi-level models, time-varying effect models, and other SEM, and importantly for the current application allows examination of relationships between multiple intensively collected variables (here affective state, mindfulness, stress, and craving) as well as moderation of these relationships by both individual-level (here treatment arm) and daily-level (session attendance, mindfulness) variables. The DSEM is specified by models at three levels. The three-level specification results from a decomposition of the observed variable(s) for a given individual at a given time (vector Y_{it}^*) into three latent, unobserved parts: an individual-specific contribution $Y_{2,i}$ a time-specific contribution $Y_{3,t}$ and a deviation for an individual, at a given time $Y_{1,it}$ ($Y_{it}^* = Y_{1,it} + Y_{2,i} + Y_{3,t}$). For example, for stress, observed weekly stress ($dStr_{it}^*$), becomes: $dStr_{it}^* = dStr_{it} + Str_i + Str_t$. These three latent components are then modeled simultaneously in a within-individual, between-individual, and between-time model. The time series describing the relationship between past and current observations in one or more intensively collected variables is modeled at the within-individual level (detailed below) The between-individual model examines influences on mean weekly stress (Str_i) and mean weekly craving as well as influences on individual-level random effects specified in the within-individual model (e.g. $\varphi_{SC,i}$: representing the relationship between weekly craving and weekly stress). The between-time model examines influences on the mean daily stress at a given time (Str_t) and on mean weekly craving at a given time (as well as influences on time-specific random effects specified at the within-individual model). For the current application, one within-individual model is a bivariate autoregressive (here specified with a lag of 1 but other lags will be explored) of weekly stress ($dStr_{it}$) and weekly craving (dCr_{it}).

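### Section 9.2 states that dynamic SEM power is unaffected by the cut from 70 daily to 8 weekly records; the simulations it cites do not reach down to 8, and precision for lagged effects must fall.

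*Combined protocol and SAP*

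**What the plan says.** Section 9.2 gives two separate power arguments for Aim 2. The parallel process growth models have a figure: 80% power with 120 individuals for an indirect effect built from correlations of 0.25 and 0.36. The DSEM has none. Its paragraph opens with a caveat, "For examining mediation/mechanistic effects at the weekly level, power is less clear", and then cites simulations in which models performed well "for a sample size of 200 individuals with a number of observations per individual ranging from 20-200", with "good model performance for all but the most complex models for smaller sample sizes". From this it concludes that "with data from 120 individuals contributing up to 8 observations each, we expect to have enough data" for the aim.

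The same section reports that the number of assessments was "reduced from 70 daily assessments to 8 weekly assessments". For the growth models it argues that power is unaffected because the calculation used individual-level latent slopes. For the DSEM it says the calculations are approximate and "were not specifically based on having daily assessments per individual so will also not change".

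Section 9.6 describes the DSEM to be fitted: a bivariate lag-1 autoregression of weekly stress and weekly craving, with person-specific random coefficients that may be related to treatment arm. The framework is chosen partly because such models "allow for a between-time level model (in addition to the between-individual level model) to incorporate time-varying effects observed in intensively collected data".

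**The concern.** Neither conclusion follows from what precedes it. A cited range of 20 to 200 records per person offers no support at 8. That a power calculation was not built on daily data does not make power independent of the number of records; it means only that the calculation did not address the matter. Information about a lag-1 coefficient comes from pairs of consecutive records, and these shrink almost tenfold.

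What is at stake is how an Aim 2 result will be read. Section 9.2 labels only Aim 3 exploratory, and section 9.6 places the DSEM under the primary analysis of Aim 2. If the plan has declared the data sufficient, a null result for arm moderation of the stress-craving link could be taken as evidence that the mechanism is absent, when the design may simply have been unable to show it.

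**Working it through.** **Inputs from the documents.** 120 analysed women and up to 8 records each (section 9.2); equal allocation (section 4.3), hence 60 per arm; 70 records under the former daily scheme (section 9.2); lag 1, random person-specific coefficients and arm as a predictor of them (section 9.6). Two-sided 0.05 is stated for Aim 1 and assumed here; 80% power is the level used throughout section 9.2.

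**Inputs not in the documents.** The between-woman SD of the lagged coefficient (tau) is varied from 0 to 0.5. Variables are standardised, so that one woman's coefficient has sampling variance of about 1/(T − 1) from T records.

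**The plan's own figures.** The growth-model power reproduces. By noncentral F with N = 120, power is 80.1% for r = 0.25 and 98.7% for r = 0.36; the product is 79.1%, against the stated 80%. This takes the slopes as given. Recruitment also reproduces: 120/(1 − 0.20) = 150. There is no DSEM figure to reproduce.

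**Position against the cited range.** 8/20 = 40% of its lower limit, and 8 is a maximum before any missed prompt. The number of women, 120, is also below the cited 200.

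**Consecutive pairs per woman.** 70 − 1 = 69 before; 8 − 1 = 7 now.

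**Detectable arm difference in a lagged coefficient.**

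MDD = (1.960 + 0.842) × sqrt[(4/120) × (tau² + 1/(T − 1))]

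Example, tau = 0:
- T = 70: 2.802 × sqrt(0.03333/69) = 0.062
- T = 8: 2.802 × sqrt(0.03333/7) = 0.193
- Ratio: sqrt(69/7) = 3.1

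| tau (assumed) | T = 70 | T = 20 | T = 8 | Ratio 8 to 70 | Ratio 8 to 20 |
|---|---|---|---|---|---|
| 0 | 0.062 | 0.117 | 0.193 | 3.1 | 1.65 |
| 0.1 | 0.080 | 0.128 | 0.200 | 2.5 | 1.56 |
| 0.2 | 0.119 | 0.156 | 0.219 | 1.8 | 1.41 |
| 0.3 | 0.165 | 0.193 | 0.247 | 1.5 | 1.28 |
| 0.5 | 0.263 | 0.281 | 0.321 | 1.2 | 1.14 |

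**Check without the closed form.** Generalised least squares information was computed from simulated bivariate lag-1 data with person-mean-centred lagged predictors, autoregression 0.3 and cross-lag 0.15 (both assumed). The 8-to-70 ratios are 3.6, 2.8, 2.0 and 1.6 for tau 0, 0.1, 0.2 and 0.3. With 20% of prompts missed they are 3.8, 3.2 and 2.4 for tau 0, 0.1 and 0.2.

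**If prompts ran for 10 weeks.** Section 5.1 spreads the 8 sessions over 10 weeks. T = 10 is still below 20, and the ratio to 70 records is 2.8 (tau 0) to 1.4 (tau 0.3) in closed form, or 3.1 to 1.5 in the simulation-based check.

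**Arm differences in mean level.** With intraclass correlation ICC and autoregression phi, a woman's mean over T records has variance proportional to

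v(T) = ICC + (1 − ICC) × ΣΣ phi^|i−j| / T²

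and the MDD ratio is sqrt[v(8)/v(70)]. For ICC 0.3 and phi 0: v(8) = 0.3 + 0.7/8 = 0.3875, v(70) = 0.3 + 0.7/70 = 0.31, and the ratio is 1.12. Over ICC 0.3 to 0.7 and phi 0 to 0.5 it runs from 1.02 to 1.26.

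**The case against.** The plan is candid in part. It says that weekly-level power is unclear, that little is known about power for such models, and that the calculations are approximate. It also gives the growth models, which do have a power figure, first place in the Aim 2 analysis. That candour stands, but it does not fit with then declaring the data sufficient and the power unchanged.

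The clause on smaller sample sizes might be read as covering 8 records. Its sentence uses sample size for the number of individuals and counts observations per individual separately, so the natural reading is fewer women. Whether the planned model is among the most complex ones simulated cannot be checked, because the documents do not list them; this point does not rely on it.

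A reader might infer that the detectable difference doubles or triples as a matter of fact. The documents do not support that. It requires tau of about 0.2 or less; the multiple is about 1.5 at 0.3 and 1.2 at 0.5, and it concerns lagged coefficients only. Section 9.6 also plans analyses of mean weekly stress and craving, for which the loss is small. A one-day and a one-week lag are also different parameters, so a larger effect at the weekly lag could offset some of the loss. The plan does not argue this, and a change of parameter is a further reason not to carry a power statement across.

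A reader might also infer an arithmetic error in the Aim 2 power. There is none: the one figure given reproduces.

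**Conclusion.** The concern holds as an unsupported adequacy statement. Three facts need no assumption: 8 is below the only range cited, pairs per woman fall from 69 to 7, and no DSEM power, effect size or detectable difference is given. Precision for the planned arm contrast in the stress-craving lagged effect therefore cannot be unaffected by the cut.

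The size of the loss does depend on assumptions: about 1.5 to 3.6 times in the detectable difference for tau 0 to 0.3, and about 1.2 times at 0.5, with 60 per arm, full response, standardised variables and equal meaning for daily and weekly lags. Missed prompts raise the multiple. No between-time random level was included in these calculations. The finding does not show that the DSEM will fail, and it does not extend to arm contrasts in mean level or to the growth-model power.

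**What to change.** In section 9.2:

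- Delete the claim that DSEM power does not change and the inference that the data are sufficient.
- State instead that power for lagged effects in the weekly DSEM has not been established at 8 records per woman, and that for an effect of given size it is lower than with 70.
- Label the DSEM analyses exploratory in sections 9.2 and 9.6, and say that a null moderation result will not be read as absence of a mechanism.

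Optionally, if the team wishes to keep a statement of adequacy, support it with a simulation of the planned model at N = 120 and T = 8 with realistic missed prompts.

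The detectable differences above should not be copied into the SAP, since they rest on assumed values. Nor does the point require a simpler two-level model: fixing the lagged effects within arm would remove the random individual effects that section 9.6 uses to relate them to other individual-level variables.

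The cost is a less favourable statement for one component of Aim 2. Enrolment, data collection and the growth-model power statement stay as they are.

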9.3 Definition of Populations

We will use an Intent to Treat model that includes all participants who complete a baseline assessment.

9.4 Interim Analyses and Stopping Rules

No interim analyses of primary and secondary data are planned for this study.

9.5 Outcomes

9.5.1 Primary Outcome

Treatment Retention. Operationalized as adherence to medication for opioid use disorder and retention in treatment over time.

Opioid use abstinence. Operationalized as number of weeks of consistent abstinence from opioids over the study period and continuity of abstinence from one assessment time point to the next.

9.5.2 Secondary Outcomes

Other substance use.

Self-reported frequency and quantity of opioid and other substance use (including alcohol, marijuana, and tobacco) will be assessed with the Alcohol, Smoking and Substance Involvement Screening Test (ASSIST), aligned with relevant timeframes (baseline: past 6 months, post-intervention and 3 month postpartum: past 3 months).

Mental Health:

Depression will be assessed using the Edinburgh Prenatal and Postnatal Depression Scales, both of which have been used extensively with the target population.

Anxiety will be assessed with the Generalized Anxiety Disorder Scale (GAD-7)², a psychometrically sound instrument routinely used in general health care settings.

Stress will be assessed with the Perceived Stress Scale,³ a psychometrically sound instrument that has been used in other studies of contemplative interventions with pregnant women⁴⁻⁷.

Posttraumatic stress will be assessed with the abbreviated PTSD Checklist (PCL-5), a screening instrument developed for primary care and other general medical settings.⁸

Mindfulness. Mindfulness will be assessed with the Mindful Attention Awareness Scale.¹³ This instrument has been used with demonstrated strong psychometrics in mindfulness intervention studies with pregnant women⁴ and substance using populations⁹⁻¹². *Acceptance* will be measured with the Acceptance and Action Questionnaire (AAQ), which has been used in other mindfulness studies with substance-using populations^{9,12}.

Quality of Life. Quality of life will be assessed with the World Health Organization QoL BRF, a widely used instrument with demonstrated validity and reliability with pregnant and early postpartum women.

Pain Perception. Pain Perception will be assessed by a widely used visual analog scale (VAS) used in other studies with pregnant women. Participants report point areas and levels of pain on a scale from 0 (no pain) to 10 (worst possible pain) and anchored with descriptive faces.

9.6 Data Analyses

Aim 1

Primary analysis: The difference between treatment arms with respect to likelihood of opioid abstinence and remaining in treatment will be evaluated by logistic generalized estimating equations (GEE). Since these binary outcomes will be evaluated at the 8-week as well as the 3-month postpartum time points, these GEE models will account for the non-independence of repeated measurements within individual. An indicator of treatment arm, time point, as well as an interaction between treatment and time point will be included as predictors in the model along with baseline covariates. Significant differences between the arms will be tested via contrasts involving the treatment*time point interaction term that compare the outcomes at each time point.

The impact of *MMORE* on treatment retention (number of weeks retained) will be evaluated via two-sample t-test if the distribution appears symmetric, but a non-parametric Wilcoxon rank sum test will be used otherwise.

Aim 2

Primary analysis: Analyses of mechanisms of effect of *MMORE* will be performed via parallel process growth models fit via structural equation models, and mediated effects between treatment assignment and outcome will be examined for the following mediator-outcome pairs: craving-abstinence, mindfulness-craving, mindfulness-treatment retention, depression-treatment retention, anxiety-treatment retention, stress-treatment retention, and mindfulness-pain. Since each mediator and outcome variable will be collected at multiple time points, latent intercept and slope effects can be estimated (as in latent growth curves). The parallel process growth models then examine mediation of the effect of an individual-level variable (treatment assignment) on the latent slope of the outcome variable by the latent slope of the mediator variable. For each mediator-outcome pair, a parallel process growth curve model will be fit including both the direct effect of treatment assignment to *MMORE* on the latent slope of the outcome, as well as the indirect effect of *MMORE* on slope of the outcome through the slope of the mediator. Estimates of path coefficients for each individual path as well as of the indirect effect along with a 95% bootstrap confidence interval will be obtained.

To examine these associations we will implement a newly developed modeling strategy called dynamic structural equation models (DSEM). DSEM like non-dynamic SEM are a modeling

framework that allows for estimating simultaneous sets of equations involving latent and observed variables, thus allowing modeling of multi-level data, and modeling relationships at each level including mediation. Unlike non-dynamic SEM, however, DSEM have the capability to estimate time-series model(s) at the within-individual level, and also allow for a between-time level model (in addition to the between-individual level model) to incorporate time-varying effects observed in intensively collected data (i.e. creating a cross-classified model). Thus DSEM combine the advantages of time-series models, multi-level models, time-varying effect models, and other SEM, and importantly for the current application allows examination of relationships between multiple intensively collected variables (here affective state, mindfulness, stress, and craving) as well as moderation of these relationships by both individual-level (here treatment arm) and daily-level (session attendance, mindfulness) variables. The DSEM is specified by models at three levels. The three-level specification results from a decomposition of the observed variable(s) for a given individual at a given time (vector Y_{it}^*) into three latent, unobserved parts: an individual-specific contribution $Y_{2,i}$ a time-specific contribution $Y_{3,t}$ and a deviation for an individual, at a given time $Y_{1,it}$ ($Y_{it}^* = Y_{1,it} + Y_{2,i} + Y_{3,t}$). For example, for stress, observed weekly stress ($dStr_{it}^*$), becomes: $dStr_{it}^* = dStr_{it} + Str_i + Str_t$. These three latent components are then modeled simultaneously in a within-individual, between-individual, and between-time model. The time series describing the relationship between past and current observations in one or more intensively collected variables is modeled at the within-individual level (detailed below) The between-individual model examines influences on mean weekly stress (Str_i) and mean weekly craving as well as influences on individual-level random effects specified in the within-individual model (e.g. $\varphi_{SC,i}$: representing the relationship between weekly craving and weekly stress). The between-time model examines influences on the mean daily stress at a given time (Str_t) and on mean weekly craving at a given time (as well as influences on time-specific random effects specified at the within-individual model). For the current application, one within-individual model is a bivariate autoregressive (here specified with a lag of 1 but other lags will be explored) of weekly stress ($dStr_{it}$) and weekly craving (dCr_{it}).

$$\begin{aligned} dStr_{it} &= \varphi_{SS,i} dStr_{it-1} + \varphi_{SC,i} dCr_{it-1} + \zeta_{S,it} \\ dCr_{it} &= \varphi_{CC,i} dCr_{it-1} + \varphi_{CS,i} dStr_{it-1} + \zeta_{C,it} \end{aligned}$$

We will obtain an estimate of the relationship between the current value of dCr and lagged value(s) of dStr ($\varphi_{CS,i}$). Moderation of this relationship by immediate contextual variables (such as weekly mindfulness value, mindfulness session attendance (among those on MMORE arm)) can be examined by including an interaction between time-varying context variables and dCr in the dStr equation. Since the regression parameters estimated are considered random individual effects, associations with other individual-level variables (such as treatment arm assignment) can be modeled in the between-individual model. This will allow us to examine moderation of the weekly relationship between dStr and dCr by individual-level variables. Mediation of the effect of immediate contextual variables on mRB by mSR will be evaluated using a cross-lagged mediation model.

Aim 3 (Exploratory). Quantitative data will be descriptively summarized, and qualitative data coded for salient themes using standard deductive methods described earlier. Data summaries will be reviewed by the Steering Committee and consultants to inform strategies to support dissemination and sustainable implementation of MMORE in women's health care settings. Data will guide interpretation of participant outcomes.

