MOUD Treatment Retention. Treatment retention will be operationalized as a composite of medication adherence (number of weeks buprenorphine or methadone present in the urine toxicology report) and treatment adherence (number of weeks attended required counseling as part of comprehensive treatment as usual, as indicated in clinical notes) - throughout the prenatal period to 3 months postpartum.

Opioid use abstinence. Weekly point of care urine toxicology screening is conducted as part of standard care with all MOUD patients at partner practices to assess for THC, cocaine, benzodiazepines, methamphetamine, opioids, methadone and buprenorphine. Opioid abstinence will be measured as number of weeks consistently abstinent from opioids over the perinatal period to 3 months postpartum.

Secondary End Points:

Other substance use. Other substance use will be measured as number of weeks the participant used marijuana and/or other drugs as indicated in urine toxicology reports. Tobacco and alcohol use will be measured by way of documentation in clinical notes from visits.

Participant Self-Report Procedures: Participants will complete secured online survey assessments at baseline, post-intervention, and 3-months postpartum. The project coordinator will ensure that participants receive the assessment surveys at the specified times in the manner preferred by the participant. If participants wish to receive the survey via email, the survey will be sent as a unique study-identified password-protected link. The project coordinator will monitor and track survey assessment completion and ensure that participants receive gift card incentives for survey completion in a timely manner. For participants who do not wish to complete the survey online, the project coordinator will arrange for either a phone interview with the participant to complete the survey or will mail the participant the survey along with a self-addressed and stamped envelope for the participant to return the survey. The assessment survey will include the following:

Primary End Points:

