9.2 Sample Size and Randomization

Sample Size.

Aim 1: For the longitudinal models of binary outcomes (abstinence, retention), assuming a within-person correlation of 0.5, there will be 80% power to detect difference between arms in the proportion retained at the 3 timepoints if the average percentage retained in the TAU arm is 60%, and the average percentage retained in the MMORE arm is 79.2%. Similar power is obtained if the TAU arm has a retention percentage of 70% while the MMORE arm has a percentage of 87% across the three timepoints. In terms of comparing abstinence longitudinally, there will be 80% power to detect a difference between arms in the percentage abstinent at the 3 timepoints if the average percentage abstinent in the TAU arm is 80% while in the MMORE arm is 94%. Power for the comparison of number of weeks abstinent during the 8-week intervention period will be 80% (at the two-sided 0.05 significance level) for differences between arms that are 0.52 times a standard deviation or more. Analyses testing for differences between arms in changes between baseline and 8-weeks, will have 80% power to detect differences that are 0.40, 0.52, and 0.61 times a standard deviation, assuming within-person correlations of 0.7, 0.5, and 0.3, respectively. We will aim to recruit 150 participants to allow for attrition (20%).

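### Opioid abstinence is defined in weeks from weekly urine screens, but section 9.6 analyses only a yes/no status at two time points, each tested with about 63-65% power rather than 80%

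*Combined protocol and SAP*

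**What the plan says.** Section 6.2 describes the data source: "Weekly point of care urine toxicology screening is conducted as part of standard care with all MOUD patients at partner practices". It then defines the endpoint: "Opioid abstinence will be measured as number of weeks consistently abstinent from opioids over the perinatal period to 3 months postpartum". Section 9.5.1 repeats the week count and adds continuity of abstinence between successive assessments.

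Section 9.2 gives two power statements for abstinence. One is for a longitudinal binary model, "assuming a within-person correlation of 0.5, there will be 80% power to detect difference between arms", with 80% versus 94% as the average rates for "a difference between arms in the percentage abstinent at the 3 timepoints". The other is for the number of weeks abstinent during the 8-week intervention period, with 80% power for a difference of 0.52 SD.

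Section 9.6 specifies a logistic GEE for abstinence and retention: "Since these binary outcomes will be evaluated at the 8-week as well as the 3-month postpartum time points". The tests are "contrasts involving the treatment*time point interaction term that compare the outcomes at each time point". The only week-count test in 9.6 is for weeks retained in treatment.

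**The concern.** The outcome is defined on a weekly series, and that series must be abstracted from charts to obtain the endpoint. The primary model then reduces it to at most two yes/no values per woman after randomisation, and nothing else in 9.6 uses weekly abstinence. The weeks-abstinent comparison that 9.2 powers has no counterpart in the analysis section.

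Two things are at stake. The primary test does not address the quantity named as the primary endpoint. And the power quoted for the binary model belongs to an average over time points, whereas the planned test looks at one time point at a time.

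**Working it through.** **Inputs.** Abstinence of 80% (TAU) and 94% (MMORE), and within-person correlation r = 0.5, from 9.2. Enrolment of 150 with 20% attrition (9.2) leaves 150 × 0.80 = 120 women. Equal allocation (4.3) gives 60 per arm. Two-sided 0.05 is stated in 9.2 for the weeks-abstinent comparison and is assumed here for the binary models.

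**Formula.** The mean of m results with exchangeable correlation r has variance factor D = [1 + (m − 1)r]/m, so the effective number per arm is n_e = 60/D. Power = Φ[(0.14 − 1.96·SE0)/SE1], where SE1 = √{[0.80·0.20 + 0.94·0.06]/n_e} and SE0 = √{2·0.87·0.13/n_e} (pooled) or SE0 = SE1 (unpooled).

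**The plan's own figure.** For m = 3 and r = 0.5, D = 0.667 and n_e = 90. SE0 = 0.0501 and SE1 = 0.0490, giving 80.3% pooled and 81.5% unpooled. The stated 80% is reproduced, as an average over three time points.

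**The contrast tested in 9.6.** For m = 1, n_e = 60, SE0 = 0.0614 and SE1 = 0.0601. Then (0.14 − 0.1203)/0.0601 = 0.327, which is 62.8% pooled; the unpooled figure is 64.5%.

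| Comparison, 80% vs 94% | D | n_e | Pooled | Unpooled |
|---|---|---|---|---|
| One time point | 1 | 60 | 62.8% | 64.5% |
| Mean of two, r = 0.5 | 0.750 | 80 | 75.4% | 76.8% |
| Mean of three, r = 0.5 | 0.667 | 90 | 80.3% | 81.5% |
| Mean of 8 weeks, r = 0.5 | 0.5625 | 106.7 | 86.5% | 87.5% |
| Mean of 8 weeks, r = 0.7 | 0.7375 | 81.4 | 76.1% | 77.5% |
| Mean of 8 weeks, r = 0.9 | 0.9125 | 65.8 | 66.9% | 68.5% |

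The retention rates in 9.2 behave alike: one time point gives 63.1% pooled and 64.7% unpooled for 60% vs 79.2%, and 62.3% and 63.9% for 70% vs 87%. A Wald test on the log-odds scale is less favourable for 80% vs 94%: 57.9% for one time point, 75.3% for three and 82.1% for eight weeks at r = 0.5.

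**If the effect builds up.** The 8-week rows assume the full 14-point difference from week 1. Suppose instead that it grows linearly to 14 points at week 8. The mean difference is 14 × 36/64 = 7.875 points. At r = 0.5 the TAU variance of the 8-week mean is 0.16 × 0.5625 = 0.0900. For MMORE it is [Σv + r((Σ√v)² − Σv)]/64, where v is each week's p(1 − p); with Σv = 0.8395 and Σ√v = 2.5624 this is 0.0579. SE = √[(0.0900 + 0.0579)/60] = 0.0496, and 0.07875/0.0496 − 1.96 is about −0.37, so power is about 35%. At r = 0.7 it is 28%. If the difference builds over 4 weeks and then holds, the mean is 91/8 = 11.375 points and power is 68%, 56% and 48% at r = 0.5, 0.7 and 0.9. The week-8 contrast stays at about 63-65% throughout.

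**The week-count comparison.** For 0.52 SD at 60 per arm, Φ(0.52·√30 − 1.96) = 81%. The statement in 9.2 is sound, but 9.6 contains no such test for abstinence.

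**The case against.** A reader might infer that weekly modelling lifts the power of the planned contrast from about 63% to 87% at no cost. The documents do not support that. The 87% belongs to a different estimand, the effect averaged over a phase; a contrast at one week stays near 63% with complete data, even inside a weekly model. Averaging alone explains much of the gain, since pooling the plan's own two time points already gives 75-77%. The 0.5 correlation is stated for three time points, not for weekly screens, which may be more alike. The constant-effect assumption is also doubtful when the sessions are spread over the same weeks (section 5.1). Nor is the change free: screens come from MOUD care, and section 2.1 cites 40% discontinuation by 3 months postpartum in one programme. Weekly results may therefore stop when a woman leaves treatment, which ties abstinence to the other primary outcome.

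A reader might also infer that the binary status rests on a single screen, so that a woman unscreened that week is lost. No section says so. The continuity wording in 9.5.1 suggests an interval, and 6.2 and 10.1 also allow self-report. The binary status is simply not defined.

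Finally, a GEE on weekly results does not itself estimate weeks of consistent abstinence.

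All of this stands, and it limits the size of the claim. It does not remove the mismatch: the endpoint is a week count, 9.2 powers a week count, and 9.6 analyses neither the count nor the series. The power of each planned contrast remains below the stated figure.

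**Conclusion.** The point holds as a mismatch between endpoint, power statement and analysis. Each single-time-point abstinence contrast in 9.6 has about 63-65% power under the plan's own rates with 60 per arm; the 80% applies only to an average over three time points at correlation 0.5. An 8-week phase average would have about 87% power at weekly correlation 0.5, 76-78% at 0.7 and 67-69% at 0.9, if the effect is constant and screens are complete. The weekly correlation and the time course of the effect are assumptions, because the documents give neither. Under gradual build-up the phase average can be the weaker test. The case for using the weekly series therefore rests first on matching the stated endpoint; the gain in power is likely only under some conditions.

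**What to change.** In 9.6, for chart-based abstinence:

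- Fit a logistic GEE to all post-randomisation weekly results, with woman as the cluster, robust standard errors, arm × phase and baseline covariates. Suitable phases are the intervention weeks, the rest of pregnancy, and birth to 3 months postpartum. Section 5.1 spreads the sessions over 10 weeks while 9.2 refers to an 8-week period; reconcile these before fixing the phase boundary.
- Name one phase contrast in advance as the test, chosen with the expected time course of the effect in mind.
- Write an explicit rule for unscreened weeks, including those after a woman leaves MOUD. The documents contain none.
- Add the weeks-abstinent comparison that 9.2 already powers.
- Keep status at 8 weeks and at 3 months postpartum as supporting results, and define how that status is derived.

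In 9.2, restate the power of the single-time-point contrasts as about 63-65%, and give the phase-average power over a range of weekly correlations and with a gradual effect.

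The cost is SAP text and programming; no new data are needed. The price is that the main reported effect becomes an average over a phase instead of status on one date.
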